10.2 Sample Size Considerations

Sample Size Considerations for Part 1

The sample size of approximately 3 to 6 subjects per monotherapy cohort is determined empirically and is consistent with those used in traditional “3+3” phase 1 designs to evaluate safety assuming a true DLT rate of less than 1/3. There are up to 4 monotherapy cohorts in Groups A / B in Part 1. Subjects enrolled in a monotherapy cohort may be replaced if they are not evaluable for DLT (eg, did not receive talimogene laherparepvec or ended the study treatment before completion of the DLT evaluation period for a reason other than experiencing a DLT). [Table 16](#) summarizes the probability of declaring a monotherapy cohort safe or unsafe for a range of true cohort DLT probabilities.

Table 16. Probability of Declaring a Monotherapy Cohort Safe or Unsafe

True Cohort DLT Probability	Probability Declare Cohort Safe	Probability Declare Cohort Unsafe
0.1	0.91	0.09
0.2	0.71	0.29
0.3	0.49	0.51
0.4	0.31	0.69
0.5	0.17	0.83

DLT = dose-limiting toxicity

Safety of the combination will be evaluated with the mTPI up-and-down design in Part 1 to determine the talimogene laherparepvec MTC with a target DLT rate of 40%. The maximum sample size in the combination cohorts 5 and 6 or 6a will be 28 (maximum of 12 DLT evaluable subjects, evaluated at 6b). Unless the cohort 5 is deemed too toxic, patients may be enrolled and assigned to appropriate doses until the maximum sample size is reached or minimum of 12 subjects are enrolled in Cohort 6 provided the mTPI outcome is not at a D or DU in cohort 6. If in HCC group, cohort 6b completes prior to cohorts 5 and 6a enrollment, and 6b is deemed safe, then cohorts 5 and 6a will close to enrollment. Full details of the mTPI will be specified in the DLRT Charter.

Table 17. mTPI Dose Decision Outcomes With a 40% Target DLT Rate^{a,b,c}

		Number of patients treated at current dose																							
		4	5	6	7	8	9	10	11	12	13	14	15	16	17	18	19	20	21	22	23	24			
Number of toxicities	0	E	E	E	E	E	E	E	E	E	E	E	E	E	E	E	E	E	E	E	E	E			
	1	S	E	E	E	E	E	E	E	E	E	E	E	E	E	E	E	E	E	E	E	E			
	2	S	S	S	S	E	E	E	E	E	E	E	E	E	E	E	E	E	E	E	E	E			
	3	D	S	S	S	S	S	S	S	S	E	E	E	E	E	E	E	E	E	E	E	E			
	4	DU	DU	D	S	S	S	S	S	S	S	S	S	E	E	E	E	E	E	E	E	E			
	5		DU	DU	DU	D	S	S	S	S	S	S	S	S	S	S	E	E	E	E	E	E			
	6			DU	DU	DU	D	D	S	S	S	S	S	S	S	S	S	S	S	E	E	E			
	7				DU	DU	DU	DU	D	D	S	S	S	S	S	S	S	S	S	S	S	S			
	8					DU	DU	DU	DU	D	D	S	S	S	S	S	S	S	S	S	S	S			
	9						DU	DU	DU	DU	DU	D	D	S	S	S	S	S	S	S	S	S			
	10							DU	DU	DU	DU	DU	DU	D	S	S	S	S	S	S	S	S			
	11								DU	DU	DU	DU	DU	DU	DU	D	S	S	S	S	S	S			
	12									DU	DU	DU	DU	DU	DU	DU	DU	D	S	S	S	S			
	13										DU	DU	DU	DU	DU	DU	DU	DU	DU	D	S	S			
	14											DU	DU	DU	DU	DU	DU	DU	DU	DU	DU	DU			
	15												DU	DU	DU	DU	DU	DU	DU	DU	DU	DU			
	16													DU	DU	DU	DU	DU	DU	DU	DU	DU			
	17														DU	DU	DU	DU	DU	DU	DU	DU			
	18															DU	DU	DU	DU	DU	DU	DU			
	19																DU	DU	DU	DU	DU	DU			
	20																	DU	DU	DU	DU	DU			
	21																		DU	DU	DU	DU			
	22																			DU	DU	DU			
	23																				DU	DU			
	24																					DU			

E = Escalate to the next higher dose
 S = Stay at the current dose
 D = De-escalate to the next lower dose
 U = The current dose is unacceptably toxic
 MTD = 40%

DLRT = Dose Level Review Team; DLT = dose limiting toxicity; MTD = Maximum tolerated dose; modified toxicity probability interval

^a Vertical axis is the maximum allowed subject incidence of DLT among the number of DLT-evaluable subjects on the horizontal axis

^b First DLRT evaluation is planned after the first 4-6 subjects have been enrolled with a minimum of 4 DLT evaluable subjects. DLRT evaluation may occur earlier at the DLRT's discretion. Please see details in the DLRT charter.

^c Sample Size = 28 across cohorts 5 and 6

Part 2 for non-HCC tumor types (Group A) or HCC (Group B) will open if the corresponding group MTC is selected at the end of Part 1.

The probability of selecting 10⁸ PFU/mL as the MTC in Part 2 for Group A/B is 97% (3% for selection of 10⁷ PFU/mL) if the true DLT rate is 10% for 10⁷ PFU/mL and 30% for 10⁸ PFU/mL, respectively (Table 17).

Table 18. MTC Selection Probabilities For True DLT Rate Scenarios

True Cohort DLT Probability		Probability of Selection		
10 ⁷	10 ⁸	10 ⁷	10 ⁸	No RP2D
0.01	0.05	0.00	1.00	0.00
0.05	0.25	0.01	0.99	0.00
0.15	0.25	0.04	0.96	0.00
0.1	0.3	0.03	0.97	0.00
0.3	0.4	0.40	0.58	0.02
0.3	0.6	0.73	0.25	0.02
0.4	0.5	0.66	0.21	0.13
0.6	0.6	0.23	0.02	0.76

DLT = dose-limiting toxicity; HCC = hepatocellular carcinoma; MTC = maximum tolerated concentration; mTPI = modified toxicity probability interval; RP2D = recommended phase 2 dose

^a Assumptions: Maximum 28 DLT-evaluable subjects in each group (non-HCC vs HCC); 40% target DLT rate; 4 additional subjects prior to each analysis.

Sample Size Considerations for Part 2

The recommended phase 2 dose from Part 1 (RP2D) for non-HCC (Group A) and HCC (Group B) will be evaluated in Part 2 independently for each tumor type arm for the combination of talimogene laherparepvec with systemic pembrolizumab. Subjects that initiate treatment at the corresponding RP2D in Part 1 will not be included in the Part 2 efficacy analysis according to their respective tumor type arm.

The primary objective in Part 2 for each tumor type arm will be to evaluate the ORR per modified irRC-RECIST with a minimum potential follow-up of at least 29 weeks. The null hypothesis (H0) for each tumor type is an ORR \leq 10% which, if true, would not warrant further evaluation in contrast to the alternative hypothesis (H1) of an ORR \geq 40%.

The following 2-stage design will be used to reject H0 at a \leq 2.5% 1-sided significance level. The efficacy analysis will be based on the Full Analysis Set in Part 2 only. A cumulative total of 10 subjects will be treated in Stage 1 and enrollment is planned to stop. If there are 2 or more responders (PR or CR no confirmation is needed), then a total of 11 additional subjects will be treated in Stage 2; otherwise, H0 will be accepted and enrollment will be permanently discontinued. If the required number of responders to continue to Stage 2 is observed before the end of Stage 1 enrollment, then enrollment will not be suspended.

H0 will be rejected after Stage 2 if there are \geq 6 responders (with confirmation) in 21 treated subjects, ie, the observed ORR is \geq 28.6%. In the event precisely 21 subjects are not included in the analysis in total, H0 will be rejected if the lower limit of the

95% exact binomial CI is $> 10\%$ (Atkinson and Brown, 1985). If exactly 10 and 11 subjects are included at Stage 1 and 2, respectively, the design achieves a 1-sided 1.3% significance level, 88.4% power, and the probability of stopping at Stage 1 if H_0 (H_1) is true is 73.6% (4.6%).

For each tumor type that advances to Stage 2, a Bayesian framework will be utilized to assess evidence that the combination ORR exceeds that expected for pembrolizumab alone to aid in decision-making as to whether further evaluation is warranted. Further detail will be described in the Statistical Analysis Plan.

From 10 to 21 subjects per tumor type are expected to be treated at the RP2D for a total of 60 to 126 subjects.

For Part 2, the DLRT will consider prospective guidelines in the DLRT Charter to monitor safety separately by tumor type arm and, if introduced, talimogene laherparepvec total volumes > 4 mL within Group A and Group B.

The subject incidence of DLT in Part 2 will be based on the DLT Analysis Set with at least 6 weeks minimum potential follow-up.

The maximum total sample size for Parts 1 and 2 is **127** subjects (**74** subjects in Part 1; **53** subjects in Part 2). Dose-limiting toxicity non-evaluable subjects will not be replaced in Part 2.

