based on the “3 + 3” design. The concentration of the first dose of talimogene laherparepvec in all cohorts will always be 10^6 PFU/mL. Maximum total volumes (up to 4 mL or 8 mL) and subsequent concentrations (10^7 or 10^8 PFU/mL) to be administered will depend on the specific cohort (refer to [Table 1](#)). Combination cohorts (Cohorts 5 and 6) in Part 1 will determine the safety of administering intrahepatic injection of talimogene laherparepvec in combination with systemic IV administration of pembrolizumab using a modified toxicity probability interval (mTPI) up-and-down design.

Table 1. Part 1 Cohort Dependencies

MONOTHERAPY COHORTS		
	DLT \geq 1/3 in 6 subjects	DLT $<$ 1/3 in 3 to 6 subjects
Group A Cohort 1	Hold study in treatment group	Open Group A Cohort 2 Open Group B Cohort 1
Non-HCC (Group A) or HCC (Group B)^a		
Cohort 1 (4 mL of 10^7 PFU/mL T-VEC)	Hold study in treatment group	Open Group B Cohort 2 ^b Open Cohort 5 in corresponding group
Cohort 2^c (4 mL of 10^8 PFU/mL T-VEC)	Open Cohort 4 
 Set MTC to 10^7 PFU/mL in monotherapy 	Open Cohort 3 
 Set MTC to 10^8 PFU/mL in monotherapy
Cohort 3^d (8 mL of 10^8 PFU/mL T-VEC)	Open Cohort 4, if: Part 2 dose for talimogene laherparepvec not determined yet OR Part 2 concentration for talimogene laherparepvec is determined to be 10^7 PFU/mL	
 Use maximum tolerated volume of 8 mL talimogene laherparepvec in Part 2
Cohort 4^e (if needed) (8 mL of 10^7 PFU/mL T-VEC)	Retain maximum volume of 4 mL talimogene laherparepvec in Part 2	Introduce volumes up to 8 mL talimogene laherparepvec in Part 2
COMBINATION COHORTS		
Non-HCC (Group A) or HCC with and without viral hepatitis (Group B)	Initial or Subsequent mTPI Outcome^f	
Cohort 5 (4 mL of 10^7 PFU/mL T-VEC + pembrolizumab)	D or DU: Stop; Hold study in treatment group S: Stay; expand cohort	E: Escalate to Cohort 6 if sample size is allowed and no DU from the previous decision.
Cohort 6 (Group A only)	DU: De-escalate to Cohort 5 and do not re-escalate D: De-escalate to Cohort 5	S or E: DLRT can declare MTC as 10^8 PFU/mL, or expand Cohort 6
Cohort 6a^g (4 mL of 10^8 PFU/mL T-VEC + pembrolizumab)	DU: De-escalate to Cohort 5 and do not re-escalate D: De-escalate to Cohort 5	S or E: DLRT can declare MTC as 10^8 PFU/mL, or expand Cohort 6a If S or E after at least 4 DLT evaluable subjects: open Cohort 6b

Table 1. Part 1 Cohort Dependencies

COMBINATION COHORTS		

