Refer to Table 1 and the Study Design and Treatment Schema at the end of the synopsis section for additional information regarding progression of the study through the monotherapy dosing cohorts in Part 1.

3.1.1.2 Part 1 Combination Cohorts: Non-HCC Subjects (Group A) and HCC Subjects With and Without Viral Hepatitis (Group B)

Safety of the combination will be evaluated with the mTPI up-and-down design in Part 1 to determine the talimogene laherparepvec MTC with a target DLT rate of 40%. A maximum of 28 DLT-evaluable subjects will be enrolled across Cohort 5 and Cohort 6 in Group A and a maximum of 28 DLT evaluable subjects will be enrolled across Cohort 5 and Cohort 6a (without viral hepatitis) in Group B. A maximum of 12 DLT evaluable subjects will be enrolled in Cohort 6b (with viral hepatitis) in Group B. The MTC used as part of the recommended phase 2 dose (RP2D) will be selected as the highest cohort concentration with an mTPI outcome of either S (stay at the current dose) or E (escalate to the next higher dose) at the last Dose Level Review Team (DLRT) analysis. Full details of the mTPI design implementation will be specified in the DLRT Charter.

Cohort 5 will begin enrollment if and when safety is established from Cohort 1 in the respective non-HCC and HCC groups. Subjects in Cohort 5 will be administered a maximum total volume of 4 mL talimogene laherparepvec in combination with pembrolizumab. The minimum and maximum number of DLT-evaluable subjects for a dose decision will be specified in the DLRT Charter. Subjects in Cohort 5 will be administered a concentration of 10^6 PFU/mL for the first cycle and 10^7 PFU/mL for talimogene laherparepvec, up to 4 mL, 21 (+ 3) days later, and Q21D (\pm 3 days) for a total of 6 cycles, with an optional 6 additional cycles (see Section 3.1.3).

Pembrolizumab at 200 mg Q3W can be administered for up to 35 cycles (approximately 24 months) (see Section 3.5.1 for additional study duration details).

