4. SUBJECT ELIGIBILITY

Investigators will be expected to maintain a screening log of all potential study candidates that includes limited information about the potential candidate (eg, date of screening, tumor type). Screening logs may be required to be shared with Amgen.

Before any study-specific activities/procedures, the appropriate written informed consent must be obtained (see Section 11.1).

As of Protocol Amendment 6 (dated 26 October 2021), intrahepatic injections of talimogene laherparepvec and liver biopsies are no longer performed in this study. Enrollment for this study has stopped.

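### Table 18's chance of ending with no Part 2 dose does not follow from Table 1: Table 1 stops Cohort 5 on D or DU, while Table 18 roughly fits a stop on DU only

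*Protocol*

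**What the plan says.** Three tables in the protocol bear on Cohort 5 (10^7 PFU/mL plus pembrolizumab).

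- **Table 1 (Section 3.1.1)** gives the conduct rule. For Cohort 5: "D or DU: Stop; Hold study in treatment group". An S expands the cohort and an E opens Cohort 6.
- **Table 17 (Section 10.2)**, titled "mTPI Dose Decision Outcomes With a 40% Target DLT Rate", turns DLT counts into decisions. With 4 subjects, 0 DLTs is E, 1 or 2 is S, 3 is D and 4 is DU. Its key reads "D = De-escalate to the next lower dose".
- **Table 18 (Section 10.2)**, "MTC Selection Probabilities For True DLT Rate Scenarios", gives the probability of selecting 10^7, 10^8 or no dose. Its footnote reads "Assumptions: Maximum 28 DLT-evaluable subjects in each group (non-HCC vs HCC); 40% target DLT rate; 4 additional subjects prior to each analysis". It does not say what a D in Cohort 5 does.

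Section 3.1.1.2 selects as MTC the highest concentration with an S or E at the last DLRT analysis. The text of Section 10.2 adds "Unless the cohort 5 is deemed too toxic, patients may be enrolled and assigned to appropriate doses", without saying whether a D counts as too toxic. Section 3.1.1.2 leaves the rest to a document outside the protocol: "Full details of the mTPI design implementation will be specified in the DLRT Charter".

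**The concern.** Cohort 5 is the lowest combination dose, so a D there has no lower dose to move to. It can be read in two ways: stop the group, or stay and enroll more. Table 1 chooses stop. The No RP2D column of Table 18 is too low for that reading whenever the true 10^7 DLT rate is 0.3 or more, so the two tables appear to describe different rules.

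If Table 1 is the real rule, the protocol understates the chance that a group ends with no Part 2 dose, including at true DLT rates at or below the 40% target. If the rule behind Table 18 is the real one, Table 1 instructs the DLRT to hold a group on a result that was meant as stay.

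**Working it through.** **Inputs.** Looks every 4 subjects and a maximum of 28 (Table 18 footnote). Start in Cohort 5; a D or DU in Cohort 6 returns to Cohort 5, with no re-escalation after DU (Table 1). 10^8 is declared once Cohort 6 has at least 12 subjects and the outcome is not D or DU (Section 10.2). The final dose needs S or E at the last look (Section 3.1.1.2). DLT counts for each decision, read from Table 17:

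| n | E | S | D | DU |
|---|---|---|---|---|
| 4 | 0 | 1–2 | 3 | 4 |
| 8 | 0–2 | 3–4 | 5 | 6+ |
| 12 | 0–2 | 3–6 | 7–8 | 9+ |
| 16 | 0–4 | 5–9 | 10 | 11+ |
| 20 | 0–5 | 6–11 | 12 | 13+ |
| 24 | 0–6 | 7–13 | none | 14+ |

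Table 17 ends at 24. For 28 subjects I assume S up to 15 DLTs and then vary that cut-off from 14 to 16.

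**Step 1: lower bound from the first look.** If D and DU both stop Cohort 5, No RP2D is at least P(X ≥ 3) with X ~ Binomial(4, p):

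- p = 0.3: 4 × 0.3³ × 0.7 + 0.3⁴ = 0.0756 + 0.0081 = 0.0837. Table 18 states 0.02 in both rows with this rate.
- p = 0.4: 4 × 0.4³ × 0.6 + 0.4⁴ = 0.1536 + 0.0256 = 0.1792. Table 18 states 0.13.

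Later looks can only add stops, so no choice of final selection rule or cut-off at 28 can bring these totals down to the stated ones.

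**Step 2: all paths.** Exact enumeration by recursive binomial sums, without simulation. Each cell gives 10^7 / 10^8 / No RP2D.

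| True DLT rates, 10^7 / 10^8 | Table 18 | Stop on D or DU (Table 1) | Stop on DU only |
|---|---|---|---|
| 0.3 / 0.4 | 0.40 / 0.58 / 0.02 | 0.336 / 0.543 / 0.121 | 0.427 / 0.553 / 0.020 |
| 0.3 / 0.6 | 0.73 / 0.25 / 0.02 | 0.654 / 0.225 / 0.121 | 0.751 / 0.229 / 0.020 |
| 0.4 / 0.5 | 0.66 / 0.21 / 0.13 | 0.482 / 0.215 / 0.303 | 0.672 / 0.218 / 0.111 |
| 0.6 / 0.6 | 0.23 / 0.02 / 0.76 | 0.135 / 0.017 / 0.848 | 0.233 / 0.017 / 0.750 |

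The extra No RP2D probability under Table 1 comes mainly out of the 10^7 column.

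**Step 3: sensitivity.** Moving the 28-subject cut-off from 14 to 16 gives No RP2D of 0.12, 0.12, 0.30–0.32 and 0.83–0.88 when D or DU stops, and 0.02, 0.02, 0.10–0.14 and 0.71–0.82 when only DU stops. Other variants were tried: dropping the 12-subject completion rule, closing Cohort 5 at 12 subjects, and different final selection rules. With D or DU stopping, the rows with a 10^7 rate of 0.3 stay near 0.12 in every one. Closing Cohort 5 at 12 brings the 0.6/0.6 row to 0.757, but leaves about 0.12 and 0.29 in the 0.3 and 0.4 rows.

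**Step 4: the other four rows.** No RP2D is at most 0.014 under either rule. At 0.1/0.3, 10^8 is selected with probability 0.962 (D or DU stops) or 0.965 (DU only), so the 97% and 3% quoted in the text cannot tell the rules apart and are essentially unaffected.

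**The case against.** Several points can be made for the plan.

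- *Table 18 states no stopping rule.* True. The DU-only rule is inferred from the figures, and the fit is approximate (0.111 against 0.13 at 0.4/0.5). The mismatch with Table 1 does not depend on that inference; Step 1 alone shows it.
- *A hold need not be final.* The DLRT may weigh all available clinical data (Section 3.1.4), and the Charter could allow a held group to resume. The protocol does not say whether a hold is permanent. But Table 1 says stop as well as hold, and the MTC needs an S or E at the last analysis, so a group left at D has no MTC.
- *The first look may come after 4 to 6 subjects (Table 17, footnote b).* With 5 evaluable subjects P(D or DU) is 0.087 at a rate of 0.4, below 0.13, so that row's lower bound depends on the look size. At a rate of 0.3 the bound is 0.031 with 5 and 0.070 with 6, still above 0.02. Table 18's own footnote sets 4.
- *Holding after 3 of 4 DLTs at the lowest dose is a sound safety choice.* It may well be. A simulation convention does not make a more cautious conduct rule wrong, so Table 1 should be changed only if the Charter shows that DU alone stopped Cohort 5.
- *The practical weight is low.* Section 4 states "Enrollment for this study has stopped", and no Part 2 analysis uses Table 18. This stands, and it limits the point to what is reported about the design.

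**Conclusion.** The concern holds. Table 18's No RP2D figures for true 10^7 DLT rates of 0.3 or more do not follow from Table 1's Cohort 5 rule. Under Table 1, a group with a true 30% DLT rate at 10^7, below the 40% target, would end with no dose about 12% of the time rather than 2%. At 40% the figure is about 30% rather than 13%, and at 60% about 85% rather than 76%. A rule in which only DU stops Cohort 5 comes close to the stated column.

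The bounds for the 0.3 and 0.4 rows rest only on Table 17 and on the 4-subject looks in Table 18's footnote, with a stop counted as No RP2D. The full-path figures also rest on the assumed cut-off at 28 subjects, which moves them little except in the 0.6/0.6 row. The documents do not show which rule the DLRT applied. The discrepancy should be corrected, but it does not affect the conduct of a trial that has finished enrolling.

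**What to change.** Confirm in the DLRT Charter what a D in Cohort 5 meant, then make one of two changes.

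- **If only DU stopped Cohort 5:** change the Table 1 cell so that DU stops and holds the group, while D or S means stay and expand the cohort.
- **If D also stopped it:** replace the last four rows of Table 18 with figures computed under that rule. On the assumptions above these are 0.34/0.54/0.12, 0.65/0.23/0.12, 0.48/0.22/0.30 and 0.14/0.02/0.85 for 10^7/10^8/No RP2D, with the Charter's cut-off at 28 subjects in place of the assumed one.

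In either case, add to Table 18's footnote the Cohort 5 rule that was simulated. The cost is a look at the Charter and one table cell or four rows, plus a footnote. Conduct does not change.

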10.3 Planned Analyses

10.3.1 Interim Analyses

Dose-limiting toxicities interim safety analyses will be performed to support the evaluation of safety and determination of the MTC and MTV of talimogene laherparepvec administered as monotherapy and in combination with systemic pembrolizumab. Interim efficacy analysis for part 1 will be performed as needed Interim safety and efficacy futility analyses are planned for this study in Part 2 separately for each tumor type arm.

10.3.1.1 DLT Safety Analysis (Part 1)

The planned interim safety data reviews for monotherapy cohorts in Part 1 to evaluate the subject incidence of DLTs will be conducted according to timing/rules described in [Table 1](#) (Section [3.1.1](#)). Data will be reviewed by a DLRT. The DLRT will recommend either to declare the cohort dose intolerable, to reassess safety after 3 additional

DLT-evaluable subjects, or to declare the cohort dose tolerable and to apply the same evaluation rules to subsequent cohorts.

For combination cohorts in Part 1, the DLRT will recommend according to the DLRT Charter whether it is safe to continue enrollment based on the mTPI up-and-down design.

10.3.1.2 Interim Safety Analysis (Part 2)

An interim safety data review will occur for each tumor type separately after approximately 10 subjects have been treated in Part 2 with the specific tumor type with at least 6 weeks of follow-up.

Additional safety analyses may be conducted as warranted during Part 2 if a DLT event occurs in the first 4 DLT-evaluable subjects or after a target of approximately 6 and 16 DLT-evaluable subjects. As appropriate the DLRT will be convened to monitor safety.

A total volume > 4 mL of talimogene laherparepvec may be allowed in Part 2 with systemic pembrolizumab if it is declared safe without pembrolizumab in Part 1. In this event, the DLRT will also monitor safety in Part 2 separately among subjects in non-HCC (Group A) and HCC (Group B) arms that receive at least 1 dose of talimogene laherparepvec with a total volume > 4 mL at the combination MTC with systemic pembrolizumab. Subjects will be included in the safety assessment of > 4 mL with at least 3 weeks follow-up from an initial total volume > 4 mL at the combination MTC.

Safety analyses, including analyses of the subjects receiving a total volume > 4 mL talimogene laherparepvec, will be performed at the time of the planned analyses for each tumor type arm or more frequently at the DLRTs discretion.

10.3.1.3 Interim Futility Analysis (Part 2)

One interim efficacy futility analysis will occur after 10 subjects have been treated with the combination in Part 2 by tumor type and have had an opportunity to be followed up for at least 20 weeks. Enrollment will be suspended for the specific tumor type pending the outcome of the interim analysis. If there are 2 or more responders (CR or PR confirmation not required), then a total of 11 additional subjects will be treated; otherwise, further enrollment of the tumor type arm will be permanently discontinued. If at least 2 responders are observed by the enrollment of the 10th treated subject, then enrollment will not be suspended.

10.3.2 Dose Level Review Team (DLRT)

A DLRT consisting of the Amgen study team, including at least one medical clinician, safety representative and biostatistician, at least one representative of the Merck study team, and at least one participating investigator who has recruited subjects into Part 1, will review the safety data to evaluate possible DLTs. Representative(s) from Merck will participate in DLRT meetings for all cohorts (voting member only for Cohorts 5 and 6 of Part 1 and all cohorts of Part 2). The DLRT will make recommendations in Part 1 and 2 according to a DLRT Charter. The DLRT Charter will include guidelines to monitor safety in Part 2 separately by tumor type arm and, if introduced, talimogene laherparepvec total volumes > 4 mL within Group A and Group B. In Part 2, the DLRT may consider reducing the RP2D talimogene laherparepvec concentration and/or discontinuation of total volumes > 4 mL, if introduced.

